### **8.2.1. Inclusion Criteria**

Patients must meet all the inclusion criteria below to be eligible for inclusion in the study:

1. *Evidence of a personally signed and dated informed consent form indicating that the patient (or his/her legal representative) has been informed of all aspects relevant to the study. Informed consent will only be obtained from patients who are still alive.*
2. *Aged 18 or over.*
3. *Histologically confirmed diagnosis of advanced kidney cancer, with at least one radiological evaluation of the disease in accordance with RECIST 1.1 criteria*

4. *Treatment with axitinib as second-line or later with a PFS equal to or greater than 9 months, or with disease progression in the first response assessment*

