## **SCHEDULE**

The administrative procedures of the study are expected to begin with the central IEC and the AEMPS in September/October 2017, with the first sites expected to open in the first quarter of 2018.

Patient recruitment will be carried out competitively for a maximum period of three months following the opening of the last participating study site. No follow-up of patients will be carried out after their inclusion in the study.

Regarding the observation period—given that it is an observational, retrospective study—this will always be prior to the inclusion of the patient in the study, with this starting at the time of diagnosis of the study condition (renal cell carcinoma) and ending at the time of inclusion in the study, or the death of the patient if this occurs first.

The study is expected to end when the data of all enrolled patients have been collected and analysed, which is estimated for 2019.

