### 6.1.2. Therapeutic approach

Until a few years ago, the only active systemic treatment available for metastatic RCC was based on immunotherapy with cytokines, IL-2 and IFN $\alpha$ , associated with a modest impact on overall survival, with a 5-year survival rate of less than 10%. However, this has dramatically changed with the development and marketing of the new targeted therapies, which have substantially modified the therapeutic approach and prognosis for these patients, from the average OS of 9.4 months described in the Motzer, et al. study to an average OS of 35.5 months in patients with anti-VEGF therapies, in progression after a first line with these targeted therapies.

This substantial progress is based on the recent advances in the understanding of the genetics and biology of RCC, which has allowed the successful development of these targeted therapies aimed at VEGF and its receptors, and the target of the rapamycin pathway. Regarding VEGF, several research lines support a unique dependence of RCC, in particular those with clear-cell histology, on this growth factor for carcinogenesis and progression.

Patients with a deletion in the VHL gene often develop multiple clear-cell tumours in their kidneys, at an early age. Similarly, the biallelic loss of the VHL gene occurs in the majority of patients who develop sporadic clear-cell RCC. This is because the VHL protein acts as a transcriptional activity regulator of the hypoxia-inducible factor (HIF), and its accumulation leads to the overexpression of multiple genes, including the gene that encodes for VEGF. VEGF binds to the receptor tyrosine kinases on the cell surface, located in the endothelial cells, to promote tumour angiogenesis and tumour proliferation.

Thus, seven molecules designed to act against specific targets and angiogenic signalling pathways have been approved in Europe and the USA, five of which target the VEGF pathway, with two targeting the rapamycin (mTOR) pathways.

In addition to these molecules, there has been the recent approval from the European Medicines Agency (EMA) and the Food and Drug Administration (FDA) of *nivolumab*, a human-IgG4 monoclonal antibody which binds to the PD-1 receptor and blocks its interaction with PD-L1 and PD-L2, thus releasing the PD-1 pathway that mediates the inhibition of immune response,

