**Analysis population****All analyses will be performed with evaluable patients.**

The CRF contains the information related to the eligibility criteria as binary variable (Yes/No) for each of the described items.

Several of these criteria can be verified with the data recorded in the CRF. This verification is performed in order to prevent the inclusion of non-evaluable participants in the statistical report and prior to the start of any analysis.

These patients will be considered screening failure, and in the statistical report they will thus be included in a table of patient disposition together with the patients screening failure initially confirmed by the sponsor.

The criteria to be verified in the patient CRFs to define the evaluable population are described below:

- An "evaluable" patient must have received at least one dose of axitinib prior to inclusion in the study: it must be verified that the "Starting dose" and the "Treatment start date with axitinib" have been specified in "Treatment with axitinib". This date must be prior to the date of signing the informed consent (for patients who are still alive at enrolment).

- Inclusion requirement *Patients must have received axitinib as second-line treatment or further line*: it must be verified that there is information concerning a first-line treatment in the "First-line treatment" section.

- IC1: *Evidence of a personally signed and dated informed consent document indicating that the patient (or his/her legal representative) has been informed of all relevant aspects of the study. Informed consent will only be obtained from patients who are still alive.*

It must be verified that the date of signing the informed consent is specified (for patients who are still alive at enrolment).

Noted that for patients already dead before the study inclusion, the CII could be "No".

- IC2: *Aged 18 or over.*

It must be verified that the age calculated with respect to the date of the baseline visit is  $\geq 18$  years.

- IC3: *Histologically confirmed diagnosis of advanced renal cell carcinoma, with at least one radiological evaluation of the disease according to RECIST 1.1 criteria.*

It must be verified that the following data have been indicated: Date of first diagnosis, Tumour stage at disease diagnosis, Date of advanced disease diagnosis, Stage of advanced disease, Metastasis location, Best treatment response (first-line treatment).

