## 7 DEFINITION OF VARIABLES AND OBJECTIVES

In addition, the following variables will be calculated from the CRF data:

NOTE: In patients with dates after the date of the IC visit / signature, the date of the IC visit / signature has been considered as the date of the last check. Due to the retrospective nature of the study, no data can be collected after the patient was included in the IC study / signature.

- Age (years) of patient at time of visit= (Visit date – Date of birth) / 365.25
- Age (years) at first diagnosis= (Date of first diagnosis – Date of birth) / 365.25
- Age (years) at the initiation of axitinib= (start date of axitinib – Date of birth) / 365.25
- Number of metastatic locations = sum (Lymph nodes, CNS, Hepatic, Pulmonary, Bone, Other).
- • Neutrophil / lymphocyte ratio. It will be categorized as follows:  $\leq 3$ ,  $> 3$ . "Before the beginning of the first line" and "At the beginning of treatment with axitinib" will be analyzed. This ratio is not calculated on axitinib suspension because there is no current lymphocyte value data in that part of the CRF.
- Time (months) between first diagnosis and nephrectomy = (Date of nephrectomy – Date of first diagnosis) / 30.4375. A list with the information (site, patient, date of first diagnosis, date of nephrectomy and the calculated time) in cases in which the time is negative (with date of nephrectomy before or equal to date of first diagnosis) will be displayed, and these cases will not be included in the descriptive analysis
- Time (months) between first diagnosis and radiotherapy = (Date of radiotherapy – Date of first diagnosis) / 30.4375. A list with the information (site, patient, date of first diagnosis, date of radiotherapy and the calculated time) in cases in which the time is negative (with date of radiotherapy before or equal to date of first diagnosis) will be displayed, and these cases will not be included in the descriptive analysis.
- Time (months) between first diagnosis and 1st-line treatment = (Date of the initiation of 1st-line treatment – Date of first diagnosis) / 30.4375. A list with the information (site, patient, date of first diagnosis, date of 1st-line treatment and the calculated time) in cases in which the time is negative (with date of 1st-line treatment before or equal to date of first diagnosis) will be displayed, and these cases will not be included in the descriptive analysis

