 $(\text{Dose increase date or Dose reduction date} - \text{Start date of treatment with axitinib}) / 30.4375$
  - Duration (months) of subsequent treatments =  
 $(\text{Date of end of subsequent treatment or of latest follow-up if not suspended} - \text{Date of start of subsequent treatment}) / 30.4375$ . In the case of several subsequent treatments per patient, proceed as follows: the duration in months of each of the subsequent treatments will be calculated (from the start date to the end date or last check if it continues). This will be done for all subsequent treatments and then proceed to make the sum per patient of all durations of subsequent treatments

- Progression-Free Survival (PFS, in months) =  
 (Date of Disease Progression on treatment with axitinib or death from any cause – Date of start of treatment with axitinib) / 30.4375  
 If there is no progression or death, the case is censored as  
 PFS (months) = (Date of latest follow-up – Date of start of treatment with axitinib) / 30.4375
- Time to progression (TTP, in months) =  
 (Date of Disease Progression – Date of start of treatment with axitinib) / 30.4375  
 If there is no progression, the case is censored as  
 TTP (months) = (Date of latest follow-up – Date of start of treatment with axitinib) / 30.4375
- Overall Survival (OS, in months) = (Date of death – Date of start of treatment with axitinib) / 30.4375  
 If death has not occurred, the case is censored as  
 Overall Survival (OS, in months) = (Date of latest follow-up – Date of start of treatment with axitinib) / 30.4375
- Overall Survival since the start of first-line treatment (OS, in months) = (Date of death – Date of start of first-line treatment) / 30.4375  
 If death has not occurred, the case is censored as  
 Overall Survival (OS, in months) = (Date of latest follow-up – Start date of first treatment) / 30.4375
- Patient subgroups
  - A-Long-term responders: comprising patients with PFS  $\geq 9$  months.
  - B-Refractory (primary): comprising patients with best response to treatment = PD. This date is collected in the CRF form “axitinib treatment”.
- MSKCC risk group (described in appendix 11.1.). It will be analysed “Before the beginning of the first line”. These calculations will be performed on patients who have data on all the variables involved (in the case of a patient who does not have data on all the variables but has > 2 factors, it will be classified in the “Poor” risk group.

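### Patients who started axitinib less than 9 months before inclusion can enter only as refractory, so the two groups cover different start-date windows; the resulting bias is probably modest but is neither checked nor mentioned

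*Protocol*

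**What the plan says.** Eligibility depends on response. Criterion 4 in Protocol 8.2.1, repeated as IC4 in SAP 2.1, takes axitinib patients in second or later line "with a PFS equal to or greater than 9 months, or with disease progression in the first response assessment". Neither the exclusion criteria nor the scope text in Protocol 8.2 sets a minimum time since axitinib start.

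The only timing check is in SAP 2.1, Analysis population, on the axitinib start date: "This date must be prior to the date of signing the informed consent (for patients who are still alive at enrolment". An interval of any length passes.

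The observation period is closed at entry. The Schedule section of the Protocol abstract has it "ending at the time of inclusion in the study, or the death of the patient if this occurs first", and adds: "No follow-up of patients will be carried out after their inclusion in the study". SAP 7 cuts later dates back to the visit or consent date because "no data can be collected after the patient was included in the IC study / signature". For PFS, SAP 7 says "If there is no progression or death, the case is censored as" the time to latest follow-up.

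The start date or calendar year of axitinib is not among the factors listed in Protocol 7.1 or SAP 7.1. Protocol 8.9 names only the uncertain patient numbers as a limitation. Protocol 8.7 allows stratified analysis in general terms without naming calendar time.

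**The concern.** Observed PFS cannot exceed the time from axitinib start to inclusion. A long-term responder therefore needs a start at least 9 months before inclusion, while a refractory patient needs only enough time for a first assessment, put at about 3 months in the SAP 5.2 definition.

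Take two patients who both start on 1 January 2018 at a site that includes patients on 1 June 2018. The one who progressed in March enters as refractory. The one still responding has 5 months of observation and cannot enter.

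The primary objective is the comparison of baseline factors between these two groups. Some of those factors could drift with time: number of previous lines, axitinib line, and prior TKI and its duration. The protocol itself describes a changing field. Section 6.1.2 says "In addition to these molecules, there has been the recent approval" of nivolumab, cabozantinib and lenvatinib, and section 6.1.3 says the last two were recently authorised after prior VEGF therapy. If such a factor differs in the latest starts, the refractory-only window would carry that difference into the comparison as an apparent association with response.

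**Working it through.** The plan gives no figure on this point to reproduce. The expected sample of about 60 is stated without a calculation (Protocol 8.5). At the stated ratio of about 2:1 it means about 40 long-term responders and 20 refractory patients.

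**Inputs from the documents**
- Earliest on-label start: 3 September 2012 (EMA) or 1 June 2014 (Spain), Protocol 6.1.4.
- Planned recruitment: 15 March to 30 September 2018, Protocol 5.

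**Assumptions**
- Axitinib starts are spread evenly over the look-back W.
- The first assessment is at t = 3 months (2 months as a variant).

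**Share of refractory patients with no possible comparator**

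Refractory starts can fall anywhere from t to W months before inclusion, and responder starts from 9 to W months. The share is (9 - t)/(W - t).

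| Start from | Inclusion at | W (months) | Share, t = 3 | Of 20 | Share, t = 2 |
|---|---|---|---|---|---|
| Sep 2012 | Mar 2018 | 66.3 | 6/63.3 = 9.5% | 1.9 | 10.9% |
| Sep 2012 | Sep 2018 | 72.9 | 6/69.9 = 8.6% | 1.7 | 9.9% |
| Jun 2014 | Mar 2018 | 45.4 | 6/42.4 = 14.1% | 2.8 | 16.1% |
| Jun 2014 | Sep 2018 | 52.0 | 6/49.0 = 12.3% | 2.5 | 14.0% |

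**Shift in mean start date**

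The group means differ by (9 - t)/2, which is 3.0 months for t = 3 and 3.5 months for t = 2, whatever W is.

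**Effect on one factor**

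The spurious difference is the share times the change in the factor's prevalence among the most recent starts. That change is an assumption.
- Suppose third-or-later-line use is 25% in older starts and 50% in the refractory-only window, with no true effect of line. At a share of 8.6% the refractory group shows 0.25 + 0.25 x 0.086 = 27.2%, an odds ratio of 1.12 against 25%. At 14.1% it shows 28.5%, an odds ratio of 1.20.
- With a 10-point change instead and W = 48 (share 6/45 = 13.3%), it shows 26.3%, an odds ratio of about 1.07.

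**Effect on the 5% test**

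This uses 20 against 40 patients, a base prevalence of 30% and a normal approximation. At a 14% share, prevalence changes of 10 to 40 points give spurious differences of 1.4 to 5.6 points. The test then rejects 5.2% to 7.6% of the time. For scale, the difference detectable with 80% power against a 50% rate is about 36 points.

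**The case against.** The strongest reply is that different start-date windows are only a precondition for bias. A factor must also differ in the last months before inclusion, and no document shows that any factor does. The approvals are undated, and one that came before the refractory-only window would affect starts open to both groups. On-label use limits drift in prior drugs, though not in number of lines. The most frequent sequence named in SAP 7.2, sunitinib-axitinib-nivolumab, places axitinib second, which does not suggest that newer agents were pushing it to late lines. All of this stands, and it limits the claim to a possible bias.

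A reader might infer a large effect by assuming that sites searched back only 24 months. The share would then be 6/21 = 29%, and the odds ratio under the 25%-to-50% assumption about 1.42. The protocol fixes no look-back, so this cannot be excluded, but nothing in it supports a limit of 24 months. It aims for the maximum possible number of patients, and section 9.1 expects many to have died before inclusion.

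A reader might also object to shorter follow-up in the refractory group, or to its larger share of the sample. Censoring and Kaplan-Meier estimation (SAP 7 and 9.1) deal with differing follow-up. The group ratio is not a population estimate, because patients between the two extremes are excluded by design.

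Finally, the study is exploratory and tests many factors without adjustment, so this is not its largest source of false positives. That bears on priority. It does not remove the asymmetry, which follows from the eligibility and observation rules alone.

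**Conclusion.** The point holds in a limited form. It is certain from the text that a start less than 9 months before inclusion leads only to the refractory group, and that no planned analysis addresses this. With the look-back of about 45 to 73 months that the documents' dates allow, about 9-14% of refractory patients, or 2-3 of about 20, have no possible comparator. This assumes uniform starts and a first assessment at 3 months. The share would be larger only with a shorter search period (or up to about 16% if the first assessment came at 2 months).

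The documents do not support saying that the comparison is confounded as a matter of fact. They make a time trend in some factors plausible but do not show one. Even with an assumed doubling of late-line use in the newest starts, the spurious odds ratio is about 1.12 to 1.20. The bias is likely modest, and a simple check is worth having.

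**What to change.** In SAP 7.1 and 9.2, add a named analysis that repeats the group comparison and the logistic model in patients of both groups whose axitinib start was at least 9 months before the inclusion or visit date. With the SAP's month length this is 9 x 30.4375 = 273.9, so 274 days. Report it beside the full-set result, and treat a factor as associated with response only if it holds in both. Add a sentence on the unequal start windows to the limitations.

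The restricted set should stand beside the full set and not replace it. The current SAP was revised on 24 October 2019 after a draft of results, and changing the main analysis set at that stage would raise its own questions. If enrolment were still open, the same condition could be added to criterion 4 for both groups.

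The cost is small. The axitinib start date is in the CRF list, and SAP 7 already uses a visit date to calculate age. That visit date does not appear in the SAP 6 variable list, and patients who had died have no consent date, so the sponsor should confirm which date serves as inclusion for them. The restricted analysis loses about 2-3 refractory patients. With 17 instead of 20 against 40 responders, the difference detectable with 80% power against a 50% rate goes from about 36 to about 38 points.

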### **8.2.2. Exclusion Criteria**

Patients who meet any of the following criteria will not be included in the study:

1. *Treatment with axitinib not accounted for in the Summary of Product Characteristics*
2. *Non-compliance with any of the study inclusion criteria*

### **8.3. Variables**

For this observational study, the following variables will be recorded: demographic, medical history (including date and stage of disease at diagnosis and at progression), surgical treatment, histology, blood count and blood biochemistry, first-line treatments, associated adverse events, clinical efficacy and history of treatment with axitinib, including treatment line (second, third, etc.), dose, reason and date of start of treatment, disease risk criteria before onset, comorbidities, associated adverse events, concomitant medication and subsequent treatments, as well as the patient’s condition (alive, deceased) and the last date on which contact was made.

A complete description of the variables, including the operational definitions, will be detailed in the Statistical Analysis Plan of the study.

### **8.4. Source documents**

The investigator will, at all times, be fully responsible for the accuracy and authenticity of all clinical and laboratory data included in the CRFs.

The source document for this study will be the medical records of the patient documented in his/her medical record, including his/her surgical records, which will be kept at the site where the study is conducted. All data will be captured in a case report form (CRF). For particular problems and/or questions or governmental requirements for an inspection, it will also be necessary to access a complete study file, provided that the patient’s right to anonymity is protected.

The information in the CRFs should be consistent with the data in the medical records.

### **8.5. Sample size**

Given the low incidence of metastatic renal cell cancer, and thus the population to be included in the study, the number of patients expected to be included will be small, and it is expected that it will be around 60 patients. However, as it is an observational and exploratory study, no hypotheses were specified and, therefore, the calculations of the sample size are not applicable.

### **8.6. Data processing**

The detailed software methodology for the handling of the data to be applied in this study will be documented in the Data Management Plan (DMP), which will be designed, filed and maintained by the sponsor. This document shall contain the details about which data (e.g. previous and concomitant medications, adverse events, etc.) will be encoded using the World Health Organization’s (WHO) Drug Reference List (DRL), which will use the Anatomical Therapeutic Chemical (ATC) classification system, or the Medical Dictionary for Regulatory Activities (MedDRA). The specific versions of the coding dictionaries used will be documented in the DMP.

### **8.7. Data Analysis**

The data will be analysed using descriptive statistics. A statistical summary will be provided including sample size, mean, standard deviation, median and range for the continuous variables, when applicable; frequency and percentages for the categorical variables. Depending on the results of interest, a stratified data analysis may be conducted. Additional exploratory analyses will be conducted, if necessary.

Details of the methodology for the summary and statistical analysis of the data collected in this study will be documented in the Statistical Analysis Plan (SAP), which will be prepared, filed and maintained by the sponsor. The SAP can modify the plans originally described in the protocol; any major change in the definitions of the study’s primary objective or analyses will be reflected as an amendment to the protocol.

